**Implementation.** We then piloted a standardized implementation protocol consisting of (a) embedding the PHQ-9 into the electronic health record (requiring the clinician to verbally assess clients as tablets were not available), (b) a site-specific guideline for PHQ-9 use, and (c) a brief training. The 4-hour training content was based on the work of Persons, Hong, and Koerner (2012); topics included: MBC as a foundational framework; MBC clinical utility; the research evidence for MBC and the PHQ-9; the MBC protocol; research and IT supports to enact the protocol; introduction to the electronic health record interface; and steps for working with lack of progress. These strategies reflect a minimum set of discrete evidence-based implementation strategies that could be blended to facilitate implementation. Pre-training Intention to Use MBC scores were highly correlated with the frequency of subsequent PHQ-9 administration ( $r=.67$ ,  $p=.036$ ). Across sites, 67% MBC penetration was achieved (number of clinicians implementing MBC/number of participating clinicians). Site A achieved 44% penetration while Site B achieved 80% penetration. One limiting factor at Site A was technology problems as the new electronic health record had not yet been introduced and the PHQ-9 did not consistently show up for clinicians. Despite these relatively high penetration scores at the clinician level, this minimal standardized implementation protocol and site-specified MBC guideline resulted in 13.4% (Site A) and 38.6% (Site B) use of the PHQ-9 (by dividing number of administrations by total possible number of administrations) over the course of one year follow up. Unfortunately, we were unable to assess the differential effect of MBC implementation on client outcomes to determine whether adapted guidelines limited MBC's utility. These findings support the proposal in three ways: (a) they emphasize the utility of a

mixed methods needs assessment in identifying site differences in barriers, (b) they highlight the importance of tailoring strategies to barriers as this minimal standardized protocol led to superior outcomes in Site B where fewer barriers were present, and, (c) they underscore the potential importance of incorporating technologically advanced solutions for client PHQ-9 completion.

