## **C12. Participants: Recruitment, Retention, and Data Collection Procedures**

### **C12a. Clinicians**

**Recruitment.** Participants will be recruited across 12 sites (Clinicians:  $N=187$ ; target:  $N=150$ ) (*Letter of Support*: CEO [name]). The number of sites and clinicians has been determined by a simulation-style power analysis to detect a small effect size predicted by previous research (*C13. Data Analysis Plan*). The main sites have been identified, but not enrolled (*Letters of Support* from regional clinic directors). As there are at least 16 sites from which to select (easily accessible from primary site) and at least 250 eligible clinicians across these sites, we are confident that we can obtain the targeted number of both sites and clinicians. Said differently, even if a site administrator enrolls a site, not all clinicians will need to participate, an important factor to avoid any perception of coercion. Given site diversity, the large number of eligible sites will maximize the likelihood that results will generalize to the broader population of community mental health centers. Sites range in size from 12 to 52 clinicians. Within each enrolled site, clinicians will have the option to participate if they (a) are at least 80% full-time equivalent (b) provide individual psychotherapy to (c) adults with depression (d) in English. These inclusion criteria reflect over 95% of clinicians at the eligible sites. Based on our pilot study, we have experienced that even those who are not supportive of MBC have agreed to participate, therefore making it unlikely that self-selection to participate would limit the generalizability of our sample. During Phase 1 (months 5-8; Table 4), clinician enrollment will begin across all sites and site randomization will occur as site level randomization improves project feasibility and reduces contamination confounds. This decision to randomize by site was also influenced by literature indicating the impact of organizational culture and climate on the implementation process (Aarons et al., 2012; Damschroder et al., 2009), which will be assessed at baseline (AT1).

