**Aim 1: Hypotheses:** Tailored implementation will outperform standardized in terms of (H1a) fidelity. MBC clinician fidelity was evaluated with two variables: (1) whether the PHQ-9 was recorded in the EHR, and (2) among encounters for which the PHQ-9 was recorded, whether it was discussed. Both outcomes were modeled using generalized linear mixed models with a logit link function for a binary distribution using the lme4 package. All models included random intercepts for clinicians and patients. Models for both outcomes were constructed in an identical sequence. Models comparisons in the model-building sequence described below were evaluated using the Bayesian Information Criterion (BIC); the model with the better BIC was selected for presentation. Several unconditional growth models (i.e., models with only parameters for time) were fit (i.e., linear, quadratic, log-transformed number of months). After establishing the unconditional growth model, additional fixed effects were added in the following sequence: (1) group main effect and (2) group x time interaction. Finally, new versus existing patient status was investigated as a main effect using a dummy variable for new patient status and as a patient status x group interaction.

**Aim 2: Hypotheses:** Contextual mediators will be leveraged in the tailored condition, but serve as barriers in the standardized condition. Mediation models were fit to evaluate which contextual factors (based on clinician-completed surveys, Table 5; and, clinician selection of drop-down menu reasons for MBC deviations captured in the electronic health record) mediate the impact of the implementation condition on both clinician- and client-level outcomes. The two critical effects underlying mediation were evaluated in separate models: treatment condition predicts the mediator (path *a*) and the mediator predicts the outcome (path *b*). Specifically, mediators were assessed at the conclusion of the implementation window and the mediators were used to predict PHQ9 completion in the sustainment window. The *a* path was assessed using linear mixed models with Satterthwaite degrees of freedom

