implemented using the R lmerTest package with a random intercept for clinic. The b path was assessed using generalized linear mixed models with a logit link function for a binary distribution using the lme4 package. **Aim 3 Hypotheses:** Adapted MBC protocols (i.e., tailored condition) will outperform routine weekly administration of PHQ-9s (i.e., standardized condition) with respect to clinically significant change in depression severity from intake to week 12. Depression severity was analyzed using linear mixed models with Satterthwaite degrees of freedom implemented using the R lmerTest package. Multiple imputation was used to estimate missing values across 20 datasets in which 22.8% of patients did not complete the 12-week interview. We first assessed whether there was a change in PHQ-9 between intake and week 12 in a mixed model containing patient status as a covariate and random intercepts for patient and clinic. Next, implementation group was added to the model. In addition, number of sessions, number of sessions that the PHQ-9 was recorded, and number of sessions that the PHQ-9 was discussed were added to the model. We also examined the interactions between new patient status and the focal variables. **Power calculations.** A power analysis for the multilevel models for Aim 1 was assessed with Monte Carlo studies in which power is the proportion of significant effects (2-tailed  $\alpha$ ,  $p < .05$ ) for parameters of interest observed over repeated analyses of simulated data (Muthén & Muthén, 2002; Thoemmes, Reiser, & MacKinnon, 2010) using MPlus (version 7). For each model, 10,000 data sets were simulated and analyzed. Data in the Monte Carlo studies were simulated with the goal of identifying the smallest detectable effect size with power  $> 80$ . Dropout was simulated to reflect an increase of 5% missing data per wave. Repeated measurements were nested within participants (ICC = .50) and participants were nested in sites (ICC = .05). Average effect sizes for Aim 1 analyses were computed using an approximation of Cohen's  $d$  for growth models (Feingold, 2009). Using this metric, we are sufficiently powered to detect effect sizes as small as  $d = .46$  for the clinician models ( $N = 150$ ) and effect sizes as small as  $d = .30$  for the client models ( $N = 500$ ). For Aim 2, we conducted power analyses for the hypothesized mediation effects with the same assumptions described above but with the use of effective samples size estimates (an ICC corrected sample size) based on a design effect adjustment (Bickel, 2007) in order to use standard effect size metrics. The  $\kappa^2$  effect size for mediation (.01, .09, and .25 represent small, medium, and large  $\kappa^2$  respectively) was computed (Preacher & Kelly, 2011). We are sufficiently powered to detect effect sizes as small as  $\kappa^2 = .16$  for the clinician models and effect sizes as small as  $\kappa^2 = .10$  for the client models. For Aim 3 analyses, we are sufficiently powered to detect effect sizes as small as  $r = .27$  for clinicians and as small as  $r = .21$  for clients. The planned sample sizes are consistently sufficient for detecting medium effect sizes for clinician outcomes and small effect sizes for client outcomes, with the power to treat site as a random effect based 6 sites per condition (Atkins & Baldwin, 2013).

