#### **C15. Justification & Feasibility.**

We selected an effectiveness-implementation hybrid to investigate one co-primary aim that focuses on (1) implementation outcomes at the clinician level and (2) effectiveness with respect to client outcomes. To test the Dynamic Sustainability Framework (Chambers et al., 2013), we will need to compare the clinical effectiveness of the adapted use of MBC (tailored) as compared to the empirically supported MBC approach (standardized). Simultaneously, because no studies have attempted to scale up MBC in community mental health, we need to evaluate the implementation (clinician-level: fidelity) outcomes. The effectiveness-implementation hybrid design type 2 was identified as the optimal and innovative design solution for this proposal.

Within the effectiveness-implementation hybrid design, we will randomize sites to condition using a dynamic waitlist controlled approach. Half of the sites will receive a standardized approach to implementation and the other half will receive a tailored approach. This design reduces the effect of management- or clinician-level readiness or client factors that might otherwise confound the training effects allowing for unbiased data (Brown, et al., 2006). This design also affords the opportunity to conduct blocking on smaller time units and statistically provides large gains in efficiency (range from 33 to 100% gains). Moreover, training efficiency is achieved as not all sites must be trained at once, therefore allowing the same trainer(s) to train all sites to reduce any possible effect at the level of trainer expertise (Herschell, Kolko, Baumann, & Davis, 2010).

We have already piloted many of the implementation strategies and the evaluation approach (*C8: Pilot Studies*). Moreover, Centerstone has successfully completed >150 studies since 2003; two of these studies were NIMH-sponsored (CATIE, Keefe et al., 2007; STAR\*D, Insel, 2006), whereas others involved wide-scale implementation of EBPs for SAMHSA-sponsored program evaluations. Co-I ([name]) has coordinated many of these multi-site clinical trials at Centerstone. This proposal’s design considerations and the established strong collaborative relationship of our investigative team, we have no concerns regarding this proposal’s feasibility.

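### Both H1a fidelity models leave out site, the unit of randomisation, so the condition effect will look more precise than it is if sites differ within condition

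*Combined protocol and SAP*

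**What the plan says.** Allocation is by site. C15 says "we will randomize sites to condition using a dynamic waitlist controlled approach", with half of the 12 sites in each condition, and C12a gives the reason that "site level randomization improves project feasibility and reduces contamination confounds".

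For Aim 1, C13a fits two binary logistic mixed models: PHQ-9 recorded at an encounter, and PHQ-9 discussed where recorded. Of both it says "All models included random intercepts for clinicians and patients". Time, then condition, then condition by time are added in sequence, and "the model with the better BIC was selected for presentation".

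The same section treats site differently elsewhere. The Aim 2 a-path model is "implemented using the R lmerTest package with a random intercept for clinic", and the Aim 3 model has "random intercepts for patient and clinic". In the power text, "participants were nested in sites (ICC = .05"), and the paragraph closes by saying that six sites per condition are enough to model site as random. None of these statements adds a site term to the H1a models.

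**The concern.** Condition varies only between sites, so the precision of the condition main effect is set by how much sites differ and by there being 12 of them. A clinician intercept allows for repeated encounters with one clinician. It does not allow for clinicians at one site resembling each other. If they do, the model counts 150 nearly independent clinicians where the design supplies 12 clusters.

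The documents give reason to expect site differences:

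- In the pilot (C9), one protocol with site-specified guidelines "resulted in 13.4% (Site A) and 38.6% (Site B) use of the PHQ-9".
- In the tailored arm (C10), each site sets its own PHQ-9 frequency, for instance monthly or every second session. Whether a PHQ-9 is recorded at a given encounter then differs by site by design, unless it is scored against the site's guideline. C11 Phase 3 points that way; the Aim 1 text does not say so.
- C12a cites organisational culture and climate as a reason for randomising by site.

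MBC fidelity is a co-primary outcome. As written, ordinary differences between sites could be reported as an effect of tailoring.

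**Working it through.** **Inputs.** From the documents: 12 sites, 6 per condition (C15); 150 clinicians, hence 150/12 = 12.5 per site; 500 clients; site ICC .05, two-sided alpha .05 and detectable d = .46 for clinician models (C13a, power). Assumed: the split of variance between site, clinician and patient on the logit scale, and the number of encounters per patient.

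**The plan's own figure.** (1.960 + 0.842) × √(2/75) = 0.4575, which rounds to .46. The figure therefore reproduces when site contributes nothing. A three-wave growth slope with complete data and within-participant ICC .50 gives the same value. With the stated site ICC in a main-effect comparison, the design effect is 1 + 11.5 × .05 = 1.575. The detectable d is then 0.4575 × √1.575 = 0.57 (normal), or 0.64 with t on 10 df. The plan's d is a growth-model metric, so this shows only that .46 needs explaining.

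**Closed form for the condition main effect.** Design effect DE = 1 + (12.5 − 1) × ICC. Type I error = 2 × [1 − Φ(1.96/√DE)]. Width of a correct interval on 10 df relative to the plan's = √DE × 2.228/1.96.

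| Site ICC | DE | Type I error | Coverage of nominal 95% CI | Width ratio |
|---|---|---|---|---|
| 0 | 1 | 5.0% | 95% | 1.14 |
| .01 | 1.115 | 6.3% | 94% | 1.20 |
| .05 | 1.575 | 11.8% | 88% | 1.43 |
| .10 | 2.15 | 18.1% | 82% | 1.67 |

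**Simulation of the logistic model as written.** 12 sites, 150 clinicians, 500 patients, 10 encounters per patient (assumed), no true condition effect, clinician and patient intercepts fitted, BIC penalty ln(5000). The site share of total latent variance is site/(site + clinician + patient + 3.29).

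| Site/clinician/patient variance | Site share of total | Wald rejection | Condition admitted by BIC | Site-level t, 10 df | Runs |
|---|---|---|---|---|---|
| 0/1/1 | 0 | 4.8% | 0.3% | 4.9% | 3,686 |
| .0526/1/1 | .010 | 10.5% (95% CI 8.7–12.5) | 1.4% | 5.3% | 1,037 |
| .278/1/1 | .050 | 23.2% (20.5–26.1) | 8.2% | 4.6% | 902 |
| .329/1.316/1.316 | .053 | 23.1% | 7.6% | 5.2% | 4,000 |
| .252/.5/1 | .050 | 28.7% | 11.3% | 5.2% | 3,219 |

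Row two reads the .05 as a share of site-plus-clinician variance (.0526/1.0526). The last three rows read it as a share of total latent variance. A second simulation of the .278/1/1 case, with 3 patients per clinician and 8 encounters each, rejected in 23.8% of runs (150 of 630), with coverage of about 76%. Without site variance it rejected in 4.7% (300 runs).

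**Adding a site intercept but keeping a Wald z-test.** Rejection was 7.2% at site variance .0526 (5.7–9.0) and 10.1% at .278 (8.2–12.2). With a t cut-off on 10 df it was 4.1% and 6.9%.

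**Plausibility of site variance.** Pilot: logit(.386) − logit(.134) = 1.40, an odds ratio of 4.1. Guideline example, assuming weekly sessions and full adherence: 25% (monthly) against 50% (every second session) is a logit gap of 1.10. Half the tailored sites on each gives site variance (1.10/2)² = .30 in that arm, a latent ICC of .046 to .084 for clinician-plus-patient variance of 3 down to 0.

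**The case against.** - **The power text shows that site was meant to be random.** This stands as evidence of intent. It is a statement about power, however, and does not override an explicit list of random effects for the H1a models. It makes the contradiction within C13a sharper.
- **The deciding parameter may be condition by time.** The power metric is for growth models and the model sequence includes that interaction. With site-intercept variance only, the interaction rejected 5.8% in 4,000 runs, so it is affected only if site trends differ. The documents do not say which term decides H1a. The condition main effect is the first term added, and the finding is limited to it.
- **Sites are matched on size and urban/rural status (C11).** The figures above ignore this. If matching balanced half the site variance, the variance factor at ICC .05 would be .95 + 12.5 × .05 × .5 = 1.26 and type I error 8.1%; at ICC .10 it would be 11.2%. Inflation disappears only if about 92% is balanced (1 − 1/12.5). The figures therefore lean high, but the direction survives.
- **The stated rule is BIC, not a .05 test.** False admission is indeed lower: 1.4% to 11.3%, against 0.3% with no site variance. BIC uses the same likelihood, however, and does nothing for the interval or p-value reported afterwards.
- **The evidence for site variance is thin.** The pilot has two sites, and Site A had technology problems. The guideline example creates variance in one arm only. Both are fair limits on the size.

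**Conclusion.** The concern holds. Two models for a co-primary outcome omit the randomised unit, in conflict with the other models and the power assumptions in the same section. If residual site variance exists, p-values and intervals for the condition main effect are anti-conservative. At the plan's own ICC of .05, type I error is about 11.8% in closed form. It is 10.5% to 29% in logistic simulation, depending on which variance the .05 refers to and on the assumed variance split and encounter counts. Matching could reduce these figures. With no site variance there is no inflation. The direction is secure; the exact size is not. The model should be corrected before the condition effect is interpreted.

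**What to change.** 1. Base inference about condition on a method suited to 12 clusters. One option is a site-level analysis with about 10 df, which held 4.6% to 5.3% in the main simulation. Another is a permutation test over the matched, cohort-restricted allocation actually used. This is the operative step, because a site intercept with a Wald z-test remained somewhat anti-conservative.
2. Add a random intercept for site to both H1a models, and a site slope for time if condition by time is interpreted. Make the Aim 1 text agree with the rest of C13a.
3. Report the condition effect and its interval whatever BIC selects.
4. State whether d = .46 refers to the condition main effect and already includes site variance. Restate it only if it does not.

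**Cost.** The analyses in C13a are written in the past tense, so this means refitting on the same data and revising the SAP wording. Intervals on 10 df are about 14% wider than from the model as written if there is no site variance, 43% wider at ICC .05 and 67% wider at ICC .10. Permutation p-values are coarse. With cohort membership held fixed and the C11 limits (first cohort 2 sites, 1–2 per condition in each cohort), cohort sizes 2, 2, 4, 4 give 2 × 2 × 6 × 6 = 144 allocations (smallest two-sided p = 2/144 = .014). Sizes 2, 3, 3, 4 give 2 × 18 × 6 = 216 (p = .009). Six matched pairs would give 2⁶ = 64 (p = .031).

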**Data Collection.** See *Table 5: Study Measures, Section II* for concise descriptions of the clinician battery. Each contextual factor of diffusion ([name] et al., 2008) will be assessed via self-report (and qualitatively via focus groups). MBC fidelity is the main clinician level implementation outcome. All clinician measures will be administered across three time points for each cohort with respect to their time since starting implementation: 1) Phase 1: Baseline Needs Assessment (AT1), prior to MBC implementation; 2) Phase 2: Implementation/Process Evaluation (AT2, 5 months in), following the active implementation phase; and, 3) Phase 3: Outcome/Impact Evaluation (AT3, 15 months in) 10 months after the research personnel have exited. Barriers to implementation will be collected for the first month of implementation via the electronic health record.

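### The Aim 1 plan lets BIC decide whether the randomised arm contrast for MBC fidelity (H1a) appears in the presented model

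*Combined protocol and SAP*

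**What the plan says.** Section A (Specific Aims) makes fidelity the clinician-level half of the single co-primary aim, and section C12a states that "MBC fidelity is the main clinician level implementation outcome".

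The Aim 1 paragraph of C13a sets two binary encounter-level outcomes: whether the PHQ-9 was recorded and, where it was, whether it was discussed. On clustering it says: "All models included random intercepts for clinicians and patients". On selection it says: "Models comparisons in the model-building sequence described below were evaluated using the Bayesian Information Criterion (BIC"), and then "the model with the better BIC was selected for presentation". The sequence that follows starts with time-only models (linear, quadratic, log months). Then "additional fixed effects were added in the following sequence: (1) group main effect and (2) group x time interaction". It ends with new-patient status and its interaction with group.

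The power paragraph of C13a treats Aim 1 as a matter of significance tests: "power is the proportion of significant effects (2-tailed", at .05) on the parameters of interest. Section C14 says that failure to support the hypothesis would still be informative.

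**The concern.** In a comparison of randomised arms, the arm contrast is the quantity the trial exists to estimate. It is normally fixed in advance and reported whatever its size. Here it sits in a list of candidate terms, behind a sentence that puts the whole list under BIC and carries the better-BIC model forward. Read as written, the presented H1a result could be a time-only model with no arm estimate and no interval.

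That outcome is most likely when the data show little difference, which is when a reader most needs the interval to judge what has been ruled out. It also sits badly with C14, since a null finding informs only if the contrast is shown. Where the arm term does survive, it has passed a screen that is not the two-tailed .05 test on which the power statement rests. The plan also does not say whether group or group x time decides H1a.

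**Working it through.** **What rests on wording alone.** The BIC sentence precedes the sequence and refers to all of it. Group and group x time are steps in that sequence. No section requires the arm estimate, its interval or its test to be reported whichever model wins. The defect follows from these facts; the arithmetic below only indicates its size.

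**The plan's own figure.** The power paragraph gives d = .46 for N = 150 clinicians with power above 80%. With 75 per arm and no site term, .46 x sqrt(75/2) = 2.817, and Phi(2.817 - 1.960) = .804. The figure is matched by this closed form. It is not a rerun of the Monte Carlo study, whose full inputs are not given. It presupposes that the arm term is tested at two-sided .05.

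**Nominal BIC cut-off.** BIC keeps a 1-df term only if its likelihood-ratio chi-square exceeds ln(n), so the nominal cut-off is P(chi-square with 1 df > ln n). The number of encounters is not in the documents, so n is an assumed range.

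| n | ln n | nominal cut-off |
|---|---|---|
| 150 | 5.01 | .025 |
| 500 | 6.21 | .013 |
| 5,000 | 8.52 | .0035 |
| 20,000 | 9.90 | .0016 |

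**Allowing for the absent site term.** These cut-offs are not real error rates, because allocation is by site and the H1a models list no site intercept. The inputs are 12 sites and 150 clinicians, hence 150/12 = 12.5 per site, with ICCs of .05 (site) and .50 (within participant) from the power paragraph. The variance of the arm effect is understated by a factor v:

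- taking .05 directly, v = 1 + 11.5 x .05 = 1.575;
- if the clinician intercept absorbs site variance, the ratio is .05/(.05 + .50) = .0909 and v = 1 + 11.5 x .0909 = 2.045.

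Under no true difference, the group step retains the term with probability 2[1 - Phi(sqrt(ln n / v))]. For an effect that a site-level t test on 10 df detects with 80% power (noncentrality 3.11), the step fails with probability Phi(sqrt(ln n / v) - 3.11). Each range below runs over the two values of v.

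| n | retained, no difference | fails, no difference | fails, 80%-power effect |
|---|---|---|---|
| 500 | .047-.081 | 92-95% | 9-13% |
| 5,000 | .020-.041 | 96-98% | 14-22% |
| 20,000 | .012-.028 | 97-99% | 18-27% |

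**Sensitivity to the benchmark.** With no site variance, and the effect set to 80% power in the fitted model's own .05 test, the group step keeps the term with probability .62 (n = 500) or .45 (n = 5,000). It then fails in 38% or 55%. The direction is the same, but the size depends heavily on the benchmark.

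**Limits.** These figures concern the group step alone. Group x time was not quantified under site clustering, because the documents give no slope variance. The ICCs were stated for repeated-wave growth models, not for binary encounter data.

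**The case against.** The strongest reply is that the authors probably meant BIC to settle the shape of time and group to stay in. The text says the terms were added, and it ends with a patient-status-by-group interaction, which normally presupposes a group main effect. Choosing a model for presentation also does not forbid reporting the comparisons. This much stands: the text permits omission and does not require it. A reader might infer that the rule removes the arm estimate whenever the result is null, and the documents do not support that. What does not stand is that the narrower intent is stated, since the BIC sentence covers the whole sequence.

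Three further inferences are tempting but unsupported.

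- **That BIC is simply a stricter test than .05.** With site omitted, false retention of the group term at n = 500 is .047 to .081, so the screen may be laxer or stricter.
- **That 92-99% of null trials would present no arm term.** That figure is for one step, and later interactions could reintroduce group.
- **That the depression outcome shows the protection fidelity lacks.** That model says only "Next, implementation group was added to the model". It sits under Aim 3, an exploratory aim, and makes no reporting commitment either.

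It is also fair to say that the missing site term is a different fault. It adds nothing to the case against the BIC rule.

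**Conclusion.** The point holds as a gap in commitment. C13a makes the H1a arm terms candidates under BIC and nowhere undertakes to report them regardless. That conclusion rests on the text and needs no assumed number.

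The size is illustrative. It assumes 500 to 20,000 encounters, the power paragraph's ICCs and equal site sizes. On those terms the group step fails in about 92-99% of trials with no difference and in roughly 9-27% with an effect that a 10-df site-level test detects with 80% power. The change should be made; it does not call the trial design into question.

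**What to change.** 1. Use BIC only to choose the form of time in the unconditional growth model.
2. For both fidelity outcomes, always fit and report the model with group and group x time, whatever its BIC.
3. Name one deciding contrast, because with group x time in the model there is no single arm odds ratio. Candidates are the arm odds ratio at "Outcome/Impact Evaluation (AT3, 15 months in) 10 months after the research personnel have exited", the arm odds ratio averaged over follow-up, or the group x time term. Report it with a 95% CI and a two-sided .05 test.
4. If the analysis has already been run, label that contrast post hoc. The past tense of C13a and its 22.8% figure for missed 12-week interviews suggest that it has.
5. Keep the patient-status terms exploratory.

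As a separate correction, add a clinic random intercept to the H1a models, as Aim 2 path a and Aim 3 already have. Use inference suited to 12 sites, for example about 10 df or a parametric bootstrap.

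The reporting change costs a few sentences, and the arm models appear to have been fitted already. The clinic intercept means re-running two models and probably accepting wider intervals. The other costs are a less parsimonious model and a deciding contrast that may have to carry a post hoc label.
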